5.3.2 Termination of Study

Although the study sponsor has every intention of completing the trial, the sponsor reserves the right to terminate the trial at any time for clinical or administrative reasons.

6. STUDY PROCEDURES/EVALUATIONS

Study visit information is listed in this section and Appendix A. Further instructions are described in the protocol-specific Manual of Procedures (MOP).

6.1 Group 1: Participants with Confirmed or Suspected Pathogen “X” Study Procedures

6.1.1 Visit 1 – Screening/Enrollment/Baseline Visit, Day 1

Sites will follow their site-specific instructions for approaching and screening potential participants for the enrollment visit. All participants successfully screened, consented, and enrolled in the study will undergo the following procedures:

- Informed consent (written, electronic or verbal) to participate in the study
- Assessment of eligibility
- Enrollment in the study
- Collection of patient information including demographics/sociodemographics, medical history, exposure history, medications, and medical record review if available
 - Sociodemographic information will include the following: age, sex, race, ethnicity, household income category, highest education achieved, previous receipt of assistance in housing or food, employment, number of persons in household, and travel history (as applicable).
- Collection of signs and symptoms of Pathogen “X” infection
- Collection of contact information
- Collection of hospitalization status (Hospitalized ICU, Hospitalized non-ICU, Outpatient)
- Physical exam may be performed to assess the need for advanced care in participants
- Vital signs³ may be collected as necessary
- Height and weight will be recorded from medical record if available
- Collection of biological specimens including:
 - Specimens from body compartment specific to Pathogen “X” to test for infection
 - 10mL blood for serum from adults
 - 2.5mL blood for serum from children

³ Temperature, heart rate, respiration rate, pulse oximetry, etc.

-
- 24mL blood for PBMCs from adults with significant anemia (Hgb<10), compromised cardiac output and/or significant respiratory compromise
 - 60mL blood for PBMCs from adults without significant anemia (Hgb≥10) and without compromised cardiopulmonary functions
 - Pediatric blood volumes for PBMCs will total ≤1 mL/kg; see MOP for specific details.
 - Collection of residuals from standard of care specimens (if available)⁴

6.1.2 Follow-up Visits

At intervals determined by the biologic characteristics of Pathogen “X” after enrollment (up to 12 months)

Participants will undergo the following procedures as necessary:

- Collection of patient information including interval medical history, medications, and medical record review if available
- Collection of signs and symptoms of Pathogen “X” infection
- Review contact information
- Physical exam may be performed to assess the need for advanced care in participants
- Vital signs may be collected as necessary
- Collection of specimens from body compartment specific to Pathogen “X”
- Collection of residuals from standard of care specimens (if available)

Participants will have the following biological specimens collected as necessary:

- Specimens from body compartment specific to Pathogen “X”
- 10mL blood for serum from adults
- 2.5mL blood for serum from children
- 24mL blood for PBMCs from adults with significant anemia (Hgb<10), compromised cardiac output and/or significant respiratory compromise
- 60mL blood for PBMCs from adults without significant anemia (Hgb≥10) and without compromised cardiopulmonary functions
- Pediatric blood volumes for PBMCs will total ≤1 mL/kg; see MOP for specific details.

⁴ Including blood, sputum, endotracheal aspirates, bronchoalveolar lavage and saliva

6.1.3 Optional Visit – Leukapheresis (Window: DPO 30 and 90)

To support development of diagnostics, therapeutics and vaccines, a subset of adult volunteers enrolled in Group 1 may undergo leukapheresis to collect additional samples for secondary research.

Leukapheresis is an outpatient procedure during which leukocytes will be selectively harvested; red cells and other blood components will be returned to the subject. In a typical leukapheresis procedure, approximately 5×10^8 to 1×10^{10} cells can be isolated with only minimal loss of red blood cells. No sedation is required. The procedure will be done by trained staff at the study site and will be done using devices and procedures that conform to standard guidelines and SOPs.

For participants consented for leukapheresis, the following screening procedures will be performed locally during the week prior to the leukapheresis procedure; fasting is not required before collection of the following:

- Collection of blood for Hgb and/or other locally required laboratories
- Conduct urine or serum pregnancy test within 48 hours of the leukapheresis procedure for women of childbearing potential. Results must be confirmed as negative prior to leukapheresis.

Refer to the protocol-specific MOP for details on the leukapheresis procedure.

6.1.4 Final Visit, DPO 365 (Window: Day 351-379)

Participants will undergo the following procedures as necessary:

- Collection of patient information including interval medical history, medications, and medical record review if available
- Review contact information
- Physical exam may be performed.
- Collection of biological specimens including:
 - Specimens from body compartment specific to Pathogen "X"
 - Collection of 10mL blood for serum from adults
 - Collection of 60mL blood for PBMCs from adults without significant anemia ($Hgb \geq 10$) and without compromised cardiopulmonary functions
 - An optional blood draw for children will occur at this visit. Collection of 2.5 mL blood for serum and blood volumes for PBMCs will total ≤ 1 mL/kg; see MOP for specific details.

6.2 Group 2: Close Contacts of Pathogen “X” Patients Enrolled in Group 1 Study Procedures

6.2.1 Screening/Enrollment/Baseline Visit, Day 1

Sites will follow their site-specific instructions for approaching and screening potential participants for the enrollment visit. All participants successfully screened, consented, and enrolled in the study will undergo the following procedures.

- Informed consent (written, electronic or verbal) to participate in the study/(and assent for participants who are children) will be obtained.
- Assessment of eligibility
- Enrollment in the study
- Collection of patient information including demographics/sociodemographics, medical history, exposure history, medications, and medical record review if available
 - Sociodemographic information will include the following: age, sex, race, ethnicity, household income category, highest education achieved, previous receipt of assistance in housing or food, employment, number of persons in household, and travel history (as applicable).
- Collection of signs and symptoms of Pathogen “X” infection
- Collection of contact information
- Physical exam may be performed to assess the need for advanced care in participants
- Vital signs⁵ may be collected as necessary
- Height and weight may be recorded from medical record if available
- Collection of biological specimens including:
 - Specimens from body compartment specific to Pathogen “X” to test for infection
 - 10mL blood for serum from adults
 - 2.5 mL blood for serum from children
 - 60mL blood for PBMCs from adults
 - Pediatric blood volumes for PBMCs will total ≤ 1 mL/kg; see MOP for specific details.

⁴Temperature, heart rate, respiration rate, pulse oximetry, etc.

6.2.2 Follow-up Visits and Final Visit

At intervals determined by the biologic characteristics after enrollment (up to 12 months)

Participants will undergo the following procedures as necessary:

- Collection of patient information including interval medical history, medications, and medical record review if available
- Collection of signs and symptoms of Pathogen “X” infection
- Review contact information
- Physical exam may be performed
- Vital signs may be collected as necessary
- Collection of specimens from body compartment specific to Pathogen “X”

Final Visit only

- Collection of biological specimens including, 10mL blood for serum from adults, 2.5 mL blood for serum from children.

6.3 Clinical Evaluations

Medical history/exposure history will be obtained by interview of the participants or by review of medical records. Participants will be queried regarding a history of signs/symptoms of Pathogen “X”. In Group 2, exposure history obtained will include whether the close contact shared a room with the index case, the number of days of exposure from initial symptoms to quarantine of the index patient, and the quarantine measures taken after diagnosis of the index case by the close contact.

At Visit 1, a physical exam may be performed based on participant’s disease severity and hospitalization status. Vital signs (temperature, heart rate, respiration rate, pulse oximetry) may be collected, as necessary. Height and weight may be collected. If not possible to obtain at enrollment, the above information may be collected by medical history.

Administration of any concomitant medications, therapies or vaccines will be documented. Concomitant medications will include all current medications and medications taken within the 30 days prior to enrollment.

Documentation of receipt of IVIG, plasma, or monoclonal antibodies or investigational immunomodulator, as described by exclusion criterion #4, will be collected at enrollment.

Group 1 patients’ disease severity will be evaluated until symptoms resolve. A final disease severity score will be assessed using the highest level of severity achieved commensurate with any scales that are developed (See Appendix B).

6.4 Laboratory Evaluations

6.4.1 Laboratory Evaluations/Assays

Laboratory testing will be conducted at potentially CLIA-certified laboratories and noncertified labs. Blood specimens and volumes will be obtained in accordance with the SOE (Appendix A). Blood specimens that will be collected as part of the standard specimen collection protocol will include serum and anticoagulated plasma both of which will be used for antibody testing and/or for measurement of circulating cytokines. Blood samples for isolation and cryopreservation of peripheral blood mononuclear cells (PBMCs) are collected for use in cellular and innate immune cell responses.

Specimens from body compartment specific to Pathogen “X” will be collected to test for Pathogen “X” detection.

Specimens will be collected for this study as indicated in the SOE and per detailed guidance provided in the MOP. Adult blood collection will not exceed 10.5 mL/kg or 550 mL, whichever is smaller, over any eight-week period. For participants with more severe Pathogen X disease, blood volumes drawn for PBMC harvests will be reduced from 60 mL to 24 mL for visits 1, 5 and 7 if the participant’s hemoglobin is ≤ 10 gm/dL, or if they have cardiogenic shock (defined as systolic blood pressure < 90 for > 30 minutes, requiring pharmacological vasopressor or mechanical support to maintain SBP > 90 , or Cardiac Index ≤ 2.2 L/min/m² and/or Pulmonary Capillary Wedge Pressure ≥ 15 mmHg), or severe hypoxemia (defined as PaO₂/FiO₂ < 100 or clinical evidence of end-organ ischemia). In addition, we will either reduce the blood volume taken to 24 mL or eliminate the PBMC blood draw on visits 1, 5 and 7, if in the opinion of the physician responsible for the participant’s care the planned blood draw would compromise the patient’s clinical status.

In accordance with US NIH recommendations, pediatric blood collection will not exceed 5 mL/kg in a single day or 9.5 mL/kg in any eight-week period.

Endpoint Assays

The specimens collected as part of this study will be available to the VTEU sites, DMID, and other interested parties as part of a specimen biobank. Certain assays may move forward as part of this study through the VTEU laboratories or IDCRC. Many of these assays may be under development across the VTEUs. With the emergence of new data, the protocol leadership and the IDCRC Leadership Group might decide to prioritize or de-prioritize some of these assays. These may include but are not limited to:

- Antibody assays:
 - Pathogen “X” neutralization assay (e.g., PRNT, FRNT)
 - Pathogen “X” pseudoneutralization assay
 - Binding antibody assays
 - Serology for related pathogens

- Pathogen “X” detection assays:
 - Pathogen “X” detection assays (e.g., PCR, culture)
- T cell responses
 - T cell ELISpot and/or ICS assays
- B Cell responses
 - Memory B cell testing
 - Plasmablast antibody secreting cells (ASCs) responses
- Innate immune responses (e.g., transcriptomics)
- Pathogen “X” whole genome sequencing (WGS)

6.4.2 Specimen Collection, Preparation, Handling and Shipping

Biosafety level 2+ will be utilized for specimen processing as recommended by Centers for Disease Control and Prevention (CDC) (e.g., handling of specimens within a biosafety cabinet, masks). Participants will be enrolled, and samples will be collected from participants by staff following current CDC requirements or local requirements (whichever is more stringent).

All specimens collected for this study will be labeled, transported, processed, tested, stored and/or shipped in accordance with site and local laboratory SOPs. The frequency of specimen collection and testing will be directed by the SOE. Additional details can be found in the protocol-specific MOP.

6.4.2.1 Instructions for Specimen Preparation, Handling and Storage

Instructions for specimen preparation, handling, and storage are included in the protocol-specific MOP.

6.4.2.2 Specimen Shipment

Instructions for specimen shipment are included in the protocol-specific MOP.

7. STATISTICAL CONSIDERATIONS

7.1 Study Hypotheses and Design

The overall objective of this prospective observational cohort study is to characterize the natural history and immune responses to Pathogen “X” infection in patients who present varying levels of disease severity and clinical symptoms, and in their close contacts. The study hypothesizes that Pathogen “X” elicits broad immune responses in individual patients, and that these responses vary over time during infection and as disease severity and symptoms progress. The study will determine whether immune responses associated with disease severity, symptoms, and demographic variables. In particular, it will focus on association with age, and consider other known or suspected factors that associate with immune responses (e.g., sex). It will also characterize spread of infection among close contacts of Pathogen “X” infected patients.

To address its objectives with adequate power, the study will target enrolling approximately 1,000 Pathogen “X” infected or suspected children and/or adult patients (Group 1) and children and/or adult close contacts of the Pathogen “X” infected patients who are enrolled in Group 1 (Group 2). Participants in Group 1 will be representative of the Pathogen “X” disease spectrum.

The primary statistical analysis of data from participants enrolled in Group 1 will be conducted using the most severe level of care (hospitalized ICU, hospitalized non-ICU, outpatients not hospitalized) received by each study participant. Secondary statistical analyses will be performed using additional disease severity scales if developed (see Appendix B).

7.2 Sample Size Considerations

The goal of the statistical analysis for the primary study objective is to study Pathogen “X”-specific binding and neutralizing antibody responses, and to determine whether these responses associate with age and disease severity. The primary and secondary analyses are mostly exploratory in nature and will use a range of descriptive statistics (e.g., mean of continuous outcome variables, correlation coefficients, proportions). Additionally, hypothesis tests will be performed to compare groups or determine whether associations between pairs of variables are significant. The following two sections evaluate the power of the study for continuous outcome variables and for response rates separately. Power calculations are also carried out anticipating that 15% of observations may be missing for any given immunological assay.

7.2.1 Power Analysis for Continuous Outcome Variables

Some statistical analyses will characterize immune responses at a given time point based on continuous outcome variables (e.g., response magnitude of Pathogen “X” specific B cells) by estimating the mean response magnitude in different groups of patients. The precision with which a mean response magnitude (more generally, the mean of a continuous outcome

variable) is estimated may be evaluated by constructing an associated two-sided 95% confidence interval. The width of these intervals is independent of the mean response magnitude but depends on the observed standard deviation of the response magnitude measurements. The half-widths of confidence intervals are reported in Table X for multiple values of the standard deviation and several group sizes [provide examples of group sizes]. The calculations assumed independent and identically normally distributed observations. [discuss results presented in table].

Table X: Half-width of two-sided 95% confidence intervals for the mean of a continuous outcome measure based on observing a particular standard deviation as a function of the sample size (n) and the observed standard deviation

std. dev.	sample size (n)					
0.10						
0.25						
0.50						
0.75						
1.0						
2.0						
5.0						
10.0						

We also evaluated the power of the study to detect statistically significant differences when comparing mean response magnitudes between two independent groups. The calculations assumed a nonparametric two-sided Wilcoxon rank sum test with a 5% significance level, and that observations are sampled from two independent and normally distributed populations. The power of the test is presented in Table X as a function of the standardized (i.e., Cohen's) effect size and of the sample sizes (n1 and n2). [discuss results presented in table]

Table X: Power for comparison of response magnitude between 2 groups of sizes n1 and n2, respectively, as a function of the standardized (Cohen's) effect size

standardized effect size		n1							
0.25	n2								
0.50	n2								
0.75	n2								
1.00	n2								

One goal of the primary objective of the study is to determine whether continuous measures of immune responses (e.g., magnitude of binding and neutralizing antibody responses to Pathogen "X" measured in blood) associate with age. These analyses may be conducted by computing correlation coefficients between immune responses and age (or any pair of continuous variables

needed to address objectives of the study). Correlation coefficients may be computed on the entire cohort or on subsets of participants (e.g., enrollment groups). The power of the study to detect a significant association between two continuous variables is shown in Table X for several values of Pearson’s linear correlation coefficient (r) and sample sizes (n).

Table X: Statistical power to detect a significant association between two continuous outcome variables (e.g., a continuous measure of an immune response and age) as a function of the sample size (n) for multiple true values of the correlation coefficient (r)

True correlation coefficient (r)	Sample size (n)						
	20	30	40	45	50	100	150
0.3							
0.4							
0.5							
0.6							
0.7							
0.8							
0.9							

7.2.2 Power Analysis for Response Rates

The immune responses will also be analyzed by estimating response rates in Group 1 overall and in subgroups of Group 1 participants defined by baseline subject characteristics such as age and disease severity. Examples of response rates include the proportion of XXX. The study may also estimate the rate of Pathogen “X” infection among Group 2 participants, i.e. close contacts of Pathogen “X”-positive enrolled subjects.

The precision with which the true response rate can be estimated from the observed data depends on the true underlying response rate and the sample size (n). Two-sided 95% confidence intervals for the response rate based on observing a particular rate of response are presented in Table X for a variety of scenarios.

Table X: Two-sided 95% confidence intervals for the true response rate based on observing a particular rate of responses

Sample size	Number of responses	Response rate	95% confidence interval (in %)

7.3 Participant Enrollment and Follow-Up

We anticipate that the study will complete enrollment in Group 1 within approximately X months upon opening. Given that many sites will enroll participants for the study, it is reasonable to expect that recruitment will be completed in fewer than X months. Every patient in Group 1 will be followed for about X years.

Subjects with close contact exposure to patients with confirmed or suspected Pathogen "X" in Group 1 and who meet the inclusion criteria will be enrolled in Group 2. We anticipate that the study will enroll 1000 participants in Group 2 (i.e., an average of 1.5 to 2 close contacts per patient enrolled in Group 1). We expect that the study will complete enrollment in Group 2 within approximately X months upon opening. Every patient in Group 2 will be followed for about X days/weeks/months.

The age of participants will be monitored during recruitment, and every effort will be made to broaden the age distribution across the Pathogen "X" disease severity spectrum.

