- Population:** Up to 1,000 participants¹ (male and female adults ≥ 18 years of age and male and female children < 18 years of age) with possible or definitive infection and/or close contacts to patients with possible or definitive infection with Pathogen "X" will be enrolled into one of two patient groups. Suspected cases may be based on appropriate exposure history and/or clinical presentation. Enrollment will be stratified by disease severity or other major categories of disease presentation as applicable.
- Group 1: Adults or children with confirmed or suspected Pathogen "X" infection representative of the disease spectrum
- Group 2: Adult or child close contacts of Pathogen "X" confirmed and/or suspected cases enrolled in Group 1
- Number of Sites:** Up to ten VTEU sites
- Study Duration:** Approximately 2 years from implementation of field activity through closure and analysis
- Participant Duration:** 12 months
- Objectives:** Primary:
- To characterize Pathogen "X" binding and neutralizing antibody responses by age and disease severity in study subjects.
 - To characterize T cell responses by age and disease severity.
 - To characterize B cell responses by age and disease severity.
 - To describe the clinical presentation and outcomes of Pathogen "X" infection in study subjects.

¹ Number of participants may be adjusted based on statistical considerations of Pathogen "X" and clinical manifestation.

Secondary:

- To describe innate immune responses to Pathogen “X”.
- To collect specimens for isolation of Pathogen “X” from body compartments pertinent to the pathogen.
- To determine rates of Pathogen “X” infection among close contacts of infected patients enrolled in Group 1.
- To determine the persistence of Pathogen “X” in whole blood, serum, urine, saliva, stool, or other body fluids as available (e.g., semen, vaginal secretions, breast milk) and characterize modes of pathogen shedding to support the development of diagnostic assays and public health prevention policy around transmission risk.

Exploratory:

- To characterize Pathogen “X”-specific immune responses other than classical antibody and T cell responses following Pathogen “X” infection to support vaccine development.
- To make available to the scientific community well-characterized specimens from Pathogen “X”-infected study subjects to facilitate development of diagnostic tests, vaccines, and therapeutics for use in other Pathogen “X” research.

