- To collect large numbers of blood immune cells by leukapheresis from selected participants to establish a specimen bank for future detailed Pathogen “X” immunological studies.
- To evaluate the associations of Pathogen “X”-specific humoral and cellular immune responses with Pathogen “X” in whole blood, serum, exosomes, urine, saliva, stool and/or other body fluids as available (e.g., semen, vaginal secretions, breast milk).
- To sequence Pathogen “X” from collected specimens (blood, body compartments specific to Pathogen “X”, etc.) in a subset of participants for the study of within-host pathogen evolution.

Description of Study Design:

[figure not shown]
This is a prospective, observational, noninterventional cohort study designed to collect clinical information and specimens to evaluate innate and adaptive immune responses of patients with confirmed Pathogen “X” and their close contacts.

Estimated Time to Complete Enrollment:

2 years. This protocol will be shelf ready for specimen collection from potentially emerging pathogens over the life cycle of the current IDCRC.

SCHMATIC OF STUDY DESIGN

Total N: Up to 1,000 participants enrolled into one of two patient groups

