4. STUDY DESIGN

This is a prospective, observational, noninterventional cohort study designed to collect clinical information and specimens to evaluate the innate and adaptive immune responses from up to 1,000 study participants. Both males and females will be screened for study interest and eligibility and enrolled, adults ≥ 18 years of age and children < 18 years of age. Two types of participants will be recruited:

- Group 1: Patients with confirmed or suspected Pathogen “X” infection, and
- Group 2: Close contacts of patients with confirmed and/or suspected Pathogen “X” infection enrolled in Group 1.

The study will ensure enrollment of patients that have clinical symptoms representative of the disease spectrum.

Group 1

Baseline data will be collected from participants with confirmed or suspected Pathogen “X” infection including demographics/sociodemographics, medical history, exposure history, medications, signs/symptoms and symptom onset date to determine the days post-illness onset (DPO). Specimens will be collected from body compartment specific to Pathogen “X”. Specimens may include whole blood, serum, urine, saliva, stool or other body fluids as available (e.g., semen, vaginal secretions, breast milk) depending on the specifics of Pathogen “X”. Specimens may be salvaged if available from standard of care testing. Clinical information and specimens will be collected at enrollment and then at an interval determined by the biologic characteristics after enrollment (up to 12 months). See Section 6 Study Procedures/Evaluations.

The association between age, severity of illness, and duration of illness on Pathogen “X” immune responses will also be explored.

An optional study visit will be conducted between DPO 30 and 90 in adult participants from Group 1 who volunteer to undergo leukapheresis. Leukocytes will be selectively harvested; red cells and other blood components will be returned to the patient. Participation will be offered to all patients and volunteers will be accepted until the spots are filled. In a typical 1½ to 3-hour leukapheresis procedure, approximately 5×10^8 to 1×10^{10} cells can be isolated with only minimal loss of red blood cells. No sedation is required. The procedure will be done by trained staff at the study site and will be done using devices and procedures that conform to standard guidelines and SOPs.

Identification of close contacts will take place as soon as possible after Group 1 participants are enrolled.

Group 2

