5. STUDY POPULATION

5.1 Selection of the Study Population

Up to 1,000 male and female participants, adults ≥ 18 years of age and children < 18 years of age, will be screened to enroll participants who meet all eligibility criteria and agree to participate.

Patients will be recruited from 10 VTEU sites and/or their sub-sites. Sites can enroll from either outpatient or inpatient sites, or both. Enrollment will be stratified by disease severity or other major categories of disease presentation as applicable. Pregnant women will not be excluded from enrollment. Blood collection volumes will be adjusted accordingly for these participants. There will not be a required sample size for this population. As this study is a descriptive study, sample size is based on feasibility instead of power for hypothesis testing.

- Group 1: Patients with confirmed or suspected Pathogen “X” infection, and
- Group 2: Close contacts of patients with confirmed and/or suspected Pathogen “X” infection enrolled in Group 1.

A subset of 10-20 adult volunteers from Group 1 will undergo leukapheresis during follow-up to compare immunological responses in those with variable severity and also to allow future comparisons with those receiving Pathogen “X” vaccines (enrolled in other studies). Study staff will inform potential participants/legally authorized representatives (LAR) of the study, obtain informed consent, and determine study eligibility. Individuals who meet all study eligibility criteria and agree to participate will be enrolled.

Usual clinical management at VTEU outpatient or inpatient sites, including standard medical care and standard therapy, will not be modified because of the study. All participants will receive appropriate treatment for Pathogen “X” that is accepted by medical experts as standard of care for the specific institution and is widely used by healthcare professionals.

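### Section 7.3 puts 1,000 participants in Group 2 alone, but the stated total for both groups is up to 1,000; the two figures cannot both hold at 1.5 to 2 contacts per case

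*Protocol*

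**What the plan says.** The design schematic gives one total for the study: "Total N: Up to 1,000 participants enrolled into one of two patient groups". The protocol summary gives the same limit for cases and close contacts together, and Section 4 plans to "evaluate the innate and adaptive immune responses from up to 1,000 study participants" before describing the two groups. Section 5.1 attaches the same number to screening: "Up to 1,000 male and female participants, adults ≥ 18 years of age and children < 18 years of age, will be screened".

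Section 7.3 gives a different picture: "We anticipate that the study will enroll 1000 participants in Group 2 (i.e., an average of 1.5 to 2 close contacts per patient". The ratio there is counted per Group 1 case.

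Section 7.1 says "the study will target enrolling approximately 1,000 Pathogen “X” infected or suspected children and/or adult patients (Group 1") and then goes on to name the close contacts of Group 2. The sentence can be read as about 1,000 across both groups, or as about 1,000 in Group 1 plus an unstated number of contacts. No separate Group 1 target is stated unambiguously anywhere.

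A footnote to the summary says: "Number of participants may be adjusted based on statistical considerations of Pathogen 'X' and clinical manifestation".

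**The concern.** Every Group 2 participant is a contact of someone enrolled in Group 1, so Group 2 cannot by itself equal the maximum for the whole study. The figure of 1,000 contacts and the total of up to 1,000 are both filled in as numbers, whereas other items in Section 7.3 (months to enroll, length of follow-up) are still marked X. A team activating the protocol would see what to complete at each X, but nothing would tell it that the Group 2 figure conflicts with the total.

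The Group 1 size is what is at stake. Section 7.1 bases the primary severity analysis on the most severe level of care received by Group 1 participants, and Section 7.2.2 estimates immune response rates in Group 1 and its subgroups. The precision and power tables of Section 7.2 are blank and have to be filled from a Group 1 size. The text supports more than one.

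**Working it through.** **Inputs.** Group 2 = 1,000 and contacts per case k = 1.5 to 2 (Section 7.3). Total = 1,000 (summary, schematic, Section 4). Missing assay data = 15% (Section 7.2).

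**Does the stated Group 2 figure fit the total?** With the total fixed, Group 1 = 1000/(1 + k) and Group 2 = 1000 − Group 1. With Group 2 fixed, Group 1 = 1000/k and total = 1000 + Group 1. If Section 7.1 means 1,000 in Group 1 alone, Group 2 = 1000 × k.

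| Starting point | k | Group 1 | Group 2 | Total |
|---|---|---|---|---|
| Total = 1,000 | 1.5 | 400 | 600 | 1,000 |
| Total = 1,000 | 2 | 333 | 667 | 1,000 |
| Group 2 = 1,000 | 1.5 | 667 | 1,000 | 1,667 |
| Group 2 = 1,000 | 2 | 500 | 1,000 | 1,500 |
| Group 1 = 1,000 | 1.5 | 1,000 | 1,500 | 2,500 |
| Group 1 = 1,000 | 2 | 1,000 | 2,000 | 3,000 |

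No row has 1,000 in Group 2 and 1,000 in total. Starting from Group 2 = 1,000, the total is exceeded by 50 to 67%. Taking 1,000 in each group does not help either: the ratio would be 1000/1000 = 1, outside 1.5 to 2, and the total would be 2,000.

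**Effect on Group 1 precision.** At a given k, the Group 1 size under Group 2 = 1,000 divided by that under total = 1,000 is:
- k = 1.5: 667/400 = 1.67
- k = 2: 500/333 = 1.5

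Confidence-interval width scales with 1/√n. Intervals under the 1,000 total are therefore wider by √1.67 = 1.29 and √1.5 = 1.22, that is by 29% and 22%.

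**Illustration only.** Take 15% missing, and assume three equally sized severity levels and 80% power; the protocol states neither assumption. Evaluable Group 1 participants are:
- Total = 1,000: 0.85 × 333 = 283 to 0.85 × 400 = 340, or 94 to 113 per level.
- Group 2 = 1,000: 0.85 × 500 = 425 to 0.85 × 667 = 567, or 142 to 189 per level.

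For a two-sided 5% Wilcoxon rank sum test on normal data, the detectable difference in SD units is d = (1.96 + 0.84) × √(2/(0.955n)), with n per level:
- n = 94: 0.42; n = 113: 0.38
- n = 142: 0.34; n = 189: 0.29

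**The case against.** The strongest defence is that this is a standby protocol for a pathogen not yet known. Its power tables are blank, several entries are still X, and the summary footnote allows the number of participants to change. Section 5.1 also says that the sample size rests on feasibility and not on power. All of this is true, and it means that 1,000 is not an immovable cap. It does not make two filled-in numbers agree. Feasibility planning needs one total as well, and Section 7.1 does claim adequate power.

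A second defence is that the choice hardly alters conclusions on the protocol's own grids. By the formula above, power at an effect size of 0.50 is about 92% or more even at 94 per level. At 0.25 it is below 80% either way (about 39 to 45% against 54 to 66%). For a correlation of 0.3, the smallest listed, power is already about 96% at n = 150. This stands: the loss is in precision and in differences between the listed values, and the power figures should not carry the point.

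Two stronger readings are tempting. A reader might infer that every primary objective would rest on only 333 to 400 cases. The objectives do not name Group 1, two of the four refer to study subjects generally, contacts found infected may contribute data, and Section 7.2.1 allows correlations on the entire cohort. The restriction to Group 1 is explicit for the primary severity analysis and for the immune response rates. A reader might also infer that filling Group 2 to 1,000 would crowd out the cases, or leave Group 1 empty. Section 4 enrolls contacts only after their Group 1 case, and at 1.5 to 2 contacts per case that cannot happen.

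**Conclusion.** The contradiction is real and lies in the current text. Section 7.3 implies 500 to 667 in Group 1 and 1,500 to 1,667 overall. The summary, schematic and Section 4 imply 333 to 400 in Group 1 and 600 to 667 in Group 2. Section 7.1 adds an ambiguity that fits neither picture if read as Group 1 alone.

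These results use only the protocol's own numbers. The consequence is a Group 1 size uncertain by a factor of 1.5 to 1.67, with intervals about 22 to 29% wider under the 1,000 total. The detectable differences of about 0.38 to 0.42 SD against 0.29 to 0.34 SD are illustrative, because they rest on assumed equal severity levels and 80% power. The documents do not show which of the two figures, the total or the Group 2 number, was intended.

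**What to change.** State separate Group 1 and Group 2 targets in the summary, Section 7.1 and Section 7.3 that agree with one total and with the contact ratio. Reword Section 7.1 so that it is clear what its 1,000 covers.

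- **If the 1,000 total is kept:** in Section 7.3 replace the 1,000 for Group 2 with about 600 to 667, and state about 333 to 400 for Group 1. This is a text edit with no extra participants.
- **If 1,000 in Group 2 is meant:** restate the total as 1,500 to 1,667 wherever 1,000 appears as the study total. That is 500 to 667 people more than the present total, with the matching site, specimen and budget load.

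In either case, fill the tables of Section 7.2 from the Group 1 size chosen, after the 15% allowance for missing assays.
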